## Safety Group

Any safety analysis, outside of safety endpoint, will be performed on the “Safety Group”. All data will be included through exit, unless a non-UroLift BPH surgical procedure (e.g. TURP, Laser, HOLEP) is performed. In these cases, follow-up safety data will be censored on the day of the alternative procedure.

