## PROTOCOL SUMMARY

Study Title:	Median Lobe Prostatic UroLift Procedure
Study Objectives:	Evaluate the safety and effectiveness of the UroLift® System when used in symptomatic benign prostatic hyperplasia (BPH) subjects with an enlarged median lobe.
Study Design:	Prospective, multicenter, non-blinded, single arm (non-randomized) study.
Sample Size:	A total of no more than 48 subjects (minimum of 40) will be enrolled.
Subject Population:	Males age of 50 years or older diagnosed with symptomatic benign prostatic hyperplasia (BPH).
Number of Centers:	A maximum of 10 investigational sites located in the US
Clinical Indication:	The UroLift System is indicated for the procedure of symptoms due to urinary outflow obstruction secondary to benign prostatic hyperplasia (BPH) in men over the age of 50.
Effectiveness Endpoint:	At 6 months, the 95% lower confidence limit of the mean percent improvement in IPSS over baseline for the UroLift system must be $\geq 25\%$ . The Lower 95% confidence Limit, determined using bootstrap method is 50.8%.
Safety Endpoint:	The composite observed rate of post-procedure device related serious complications less than or equal to 15% at 3 months. Composite device related serious complications for this endpoint are 1) De Novo (new) severe urinary retention lasting more than 21 consecutive days post procedure, 2) Device related formation of fistula between the rectum and urethra, and 3) perforation of the rectum or GI tract, 4) damage to ureter or ureteral orifices 5) damage to the trigone requiring surgical repair or 6) de novo , sustained erectile dysfunction.
Additional Assessments:	Over the 12 month follow-up period, lower urinary tract symptoms (LUTS), quality of life (QOL), recovery, uroflowmetry, PVR, proportion of subjects who experience de novo sustained erectile dysfunction and anejaculation through 12 months, number of subjects with encrusted implants, patient satisfaction and adverse events severity and relatedness will be assessed.

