## Intention to Treat Group

The main analyses, including endpoints, will be performed on the “intent-to-treat (ITT)” group. All subjects who are enrolled will be included in the intention to treat analysis. With the ITT analysis, primary outcome data from subjects retreated with either the UroLift System or with any other surgical procedure will be censored the day after the alternative procedure. Additionally, subjects that start on alpha blockers or 5ARI medications specifically for the treatment of BPH, and use then consistently will have their results censored the day after starting this medication. Consistent usage is defined any medication use for more than 60 days.

The IIT population is used for efficacy analyses.

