## Evaluation of Safety Endpoint

The composite observed rate of post-procedure device related serious complications less than or equal to 15% at 3 months. Composite device related serious complications for this endpoint are 1) de Novo (new) severe urinary retention lasting more than 21 consecutive days post procedure, 2) formation of fistula between the rectum and urethra, and 3) perforation of the rectum or GI tract, 4) damage to ureter or ureteral orifices 5) damage to the trigone requiring surgical repair or 6) de novo, sustained erectile dysfunction.

The CEC will determine if any adverse events reported through 3 months post-index procedure qualify to meet the 6 elements of the composite safety endpoint. The observed rate of the six serious complications must be less than or equal to 15% for the trial to be successful.

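### Censoring safety data on the day of non-UroLift BPH surgery leaves late device-related events in those men out of every safety analysis except the 3-month composite

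*Combined protocol and SAP*

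**What the plan says.** The Safety Group section sets the scope: "Any safety analysis, outside of safety endpoint, will be performed on the “Safety Group". It then gives the rule and its one exception: "All data will be included through exit, unless a non-UroLift BPH surgical procedure (e.g. TURP, Laser, HOLEP) is performed". For men who meet the exception, "In these cases, follow-up safety data will be censored on the day of the alternative procedure".

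The Protocol Summary gives the purpose of the study as: "Evaluate the safety and effectiveness of the UroLift® System when used in symptomatic benign prostatic hyperplasia (BPH) subjects with an enlarged median lobe". Its Additional Assessments, over 12 months, include de novo sustained erectile dysfunction and anejaculation, and "number of subjects with encrusted implants, patient satisfaction and adverse events severity and relatedness will be assessed".

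Two neighbouring rules matter for comparison. In the Intention to Treat Group section, primary outcome data after retreatment "will be censored the day after the alternative procedure", and there the trigger is either UroLift retreatment or any other surgery. In Evaluation of Safety Endpoint, the composite has its own process: "The CEC will determine if any adverse events reported through 3 months post-index procedure qualify".

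No section keeps device-related events after the alternative operation, lists them separately, or plans an analysis that includes them.

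**The concern.** The product is an implant. The documents do not say that a later TURP, laser or HoLEP removes every implant or ends its effects, so an event after that operation can still be caused by the device. Under the rule such an event is not analysed.

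The lost follow-up is not a random sample of follow-up. It comes only from men who needed another BPH operation, a group in which late device-related problems are plausibly more common. Censoring of that kind is informative, and it tends to make device-related rates look lower than they are. At stake is the 12-month safety description in men with an enlarged median lobe, which is half of the stated objective.

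**Working it through.** **What the rule drops and keeps.** This comes from reading the sections side by side.

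- Events before the alternative operation: kept, because the rule acts only from that day.
- Events after the day of the operation: dropped, whatever their cause.
- Events found on the day itself: probably dropped. The Safety Group rule censors on the day, while the Intention to Treat rule censors the day after. The contrast suggests that the day of surgery is excluded, but the text does not say so. It also does not say whether an event is dated by onset or by discovery.
- Men retreated with UroLift or started on BPH drugs: not censored for safety, because only non-UroLift surgery triggers the rule.
- Encrusted implants: Summary of Procedures schedules one follow-up cystoscopy, at 6 months. A man who has other surgery before then has that examination excluded from the analysis, if the count is treated as a safety analysis.

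**Inputs.** Enrolment is 40 to 48 men in a single arm, followed for 12 months (Protocol Summary). The documents give no rate or timing of surgical crossover, so those values are assumed below. The plan has no figure of its own on this point to reproduce.

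**Step 1: weight of one man.** 1/40 = 2.5%; 1/48 = 2.1%.

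**Step 2: effect of keeping one or two events that the rule would drop.** Assume that no other event of that type occurs. The one-sided 95% exact (Clopper-Pearson) upper limit for x events in n men is the 0.95 quantile of Beta(x + 1, n − x). For x = 0 this is 1 − 0.05^(1/n).

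| Events reported | n = 40: rate (upper limit) | n = 48: rate (upper limit) |
|---|---|---|
| 0 | 0% (7.2%) | 0% (6.1%) |
| 1 | 2.5% (11.3%) | 2.1% (9.5%) |
| 2 | 5.0% (14.9%) | 4.2% (12.5%) |

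**Step 3: follow-up lost.** With m men censored at month t, the share of planned person-time lost is m × (12 − t) / (12 × n). Crossover of 2.5%, 5% or 10% and surgery at month 3, 6 or 9 are assumptions. The number of men is rounded.

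| n | Crossover | m | Month 3 | Month 6 | Month 9 |
|---|---|---|---|---|---|
| 40 | 2.5% | 1 | 9/480 = 1.9% | 6/480 = 1.25% | 3/480 = 0.6% |
| 40 | 5% | 2 | 18/480 = 3.75% | 12/480 = 2.5% | 6/480 = 1.25% |
| 40 | 10% | 4 | 36/480 = 7.5% | 24/480 = 5.0% | 12/480 = 2.5% |
| 48 | 2.5% | 1 | 9/576 = 1.6% | 6/576 = 1.0% | 3/576 = 0.5% |
| 48 | 5% | 2 | 18/576 = 3.1% | 12/576 = 2.1% | 6/576 = 1.0% |
| 48 | 10% | 5 | 45/576 = 7.8% | 30/576 = 5.2% | 15/576 = 2.6% |

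The time lost is small, 0.5% to 7.8% over this range. Step 2 shows why it can still matter: in a cohort this size, one dropped event can be the difference between reporting none and reporting some.

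**The case against.** The strongest defence is confounding. In a single-arm study, a TURP or laser procedure can itself cause bleeding, retention, erectile dysfunction or loss of ejaculation, and the sponsor has good reason not to charge that harm to the implant. This stands for outcomes counted per subject, such as de novo sustained erectile dysfunction and anejaculation, where event-level attribution does not settle the matter. It does not justify dropping every event. The Protocol Summary already says that "patient satisfaction and adverse events severity and relatedness will be assessed", and Summary of Procedures collects adverse events and interventions through the 12-month visit.

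A second defence is that attribution after another operation may be difficult. The documents do not say what relatedness is judged against or by whom, and they describe CEC review only for the composite through 3 months. This also stands, as a cost of the fix.

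A reader might infer more than the text supports:

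- **That the rule removes these men from the safety analysis.** It does not. Harm recorded before the operation, including harm that led to it, stays in.
- **That it removes all device failures.** It reaches only failures that led to non-UroLift surgery.
- **That harm found during the second operation is certainly lost.** That is the likelier reading of an ambiguous phrase, not a stated rule.

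**Conclusion.** The point holds in limited form. As written, device-related events after non-UroLift BPH surgery are left out of all safety analyses other than the 3-month composite, through a trigger related to device failure. The likely direction is that 12-month device-related rates are understated. The amount cannot be computed and could be zero if no such event occurs. It depends on how many men cross over, when they do so, and whether device-related events follow. The crossover rates and times used in the check are assumptions, not estimates.

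It would be tempting to conclude that the rule threatens the trial's result. The documents do not support that. The effectiveness test uses IPSS at 6 months under separate rules, and the 15% safety criterion is expressly outside the Safety Group rule. What is affected is the descriptive safety profile. A change is worth making, but this is not a fatal defect.

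**What to change.** Amend the Safety Group section as follows.

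1. Include safety data through study exit for every man, whether or not he has another BPH procedure.
2. Count events judged related to the UroLift device or index procedure in the main device-related tables, including those on or after the day of the alternative surgery.
3. List all other events on or after that day separately, so that harm from the second operation is visible but not charged to the device.
4. Keep the censored analysis as a sensitivity analysis. State whether the day of surgery is included and whether events are dated by onset or by discovery.
5. Show de novo sustained erectile dysfunction and anejaculation with and without censoring.
6. State who judges relatedness after a second operation, and that each event is judged against both the UroLift device or procedure and the later surgery.

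The cost is SAP wording, one listing and a repeat of some tables. Adverse events, relatedness and interventions are already to be collected through 12 months. The downside is that some events will be hard to attribute, and reported device-related rates may rise slightly.

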## Evaluation of Primary Effectiveness Hypothesis

If the lower limit of the one-sided 95% confidence interval for mean IPSS percentage change for the UroLift system at 6 months is greater than or equal to 25%, then the null hypothesis will be rejected in favor of the alternative hypothesis. (The lower 95% confidence limit, determined using bootstrap method is 50.8%.)

Subjects who have missing IPSS data due to lost to follow-up will have the percent change from baseline at 6 months value imputed using the MCMC (Markov Chain Monte Carlo) multiple imputation method. Partially completed IPSS questionnaires will also be considered missing. The lower bound of the one-sided 95% confidence interval will be constructed using the mean and standard error from the MCMC method.

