## Sample Size Estimate

From a practical perspective, the sample size estimate can be based on the number of expected subjects that could have been included in the UroLift pivotal trial (L.I.F.T.) had subjects with median lobe been allowed to enroll. To statistically corroborate the sample size estimate, an evaluation of the IPSS response in the L.I.F.T. treatment arm at 6 months was evaluated. Taking this value and applying a lower confidence bound, the estimated mean IPSS response for this study was determined.

For a one-sided 95% confidence interval, based on a t-test, the sample size estimate was calculated.

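### Does the 50.8% bootstrap limit printed beside the success criterion give the primary bound a second construction?

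*Combined protocol and SAP*

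**What the plan says.** The section Evaluation of Primary Effectiveness Hypothesis states the rule and gives the side of the limit: "If the lower limit of the one-sided 95% confidence interval for mean IPSS percentage change". The trial succeeds on effectiveness when that limit is 25% or more at 6 months. A parenthesis follows: "The lower 95% confidence limit, determined using bootstrap method is 50.8" per cent. The next paragraph has missing 6-month values imputed by MCMC multiple imputation and then says how the bound is formed: "The lower bound of the one-sided 95% confidence interval will be constructed using the mean and standard error from the MCMC method".

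The effectiveness endpoint in the Protocol Summary opens with "At 6 months, the 95% lower confidence limit of the mean percent improvement in IPSS over baseline for the UroLift system must be" at least 25%. It then repeats the bootstrap sentence, "The Lower 95% confidence Limit, determined using bootstrap method is 50.8" per cent. It gives no side for the limit and does not mention imputation.

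The Sample Size Estimate section bases the planning mean on the 6-month response in the pivotal trial's treatment arm: "Taking this value and applying a lower confidence bound, the estimated mean IPSS response for this study was determined". It sizes the study on a one-sided 95% interval from a t-test. It prints no planning mean and mentions neither the bootstrap nor 50.8%.

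**The concern.** A bootstrap limit and a limit built from a pooled multiple-imputation mean and standard error are different calculations. Both appear next to the same criterion, and the only numerical value printed for a limit is the bootstrap one. Someone who reads only the Protocol Summary could take the bootstrap to be the primary method and would not learn that the limit is one-sided.

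If the plan really allowed two constructions, the choice could be made after seeing the data, and the trial's single effectiveness decision would not be fully pre-specified. Nor can the origin of 50.8% be traced: the documents give no data set, sample size, bootstrap variant or handling of missing values for it.

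**Working it through.** **1. Can 50.8% be reproduced?** No. The documents give no mean, SD, sample size or data set for it. Only range checks are possible, and every SD and missing fraction below is an assumption.

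**2. What could the number be?**

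- *A planning mean.* The distance to the goal is 50.8 − 25 = 25.8 points. For a one-sample, one-sided t-test at 0.05, the sample size for 80%/90% power is 10/14 at SD 30, 17/23 at SD 40, 25/34 at SD 50 and 35/48 at SD 60. The planned 40–48 subjects neither confirm nor exclude this reading, because the Sample Size Estimate section also justifies the number on practical grounds.
- *This trial's one-sided limit.* The implied mean is 50.8 + t(0.95, n−1) × SD/√n. At n = 40, SD 30 this is 50.8 + 1.685 × 4.743 = 58.8%. Over n = 40–48 and SD 20–40 the range is about 56–62%, which is also possible.
- *A supportive or complete-case bootstrap value from this trial.* Nothing in the text rules this out.

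The documents do not settle which reading is right. Under the first and third, the imputation-based bound is plainly the only decision bound. Under the second, the text still contains only one instruction for constructing it.

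**3. What do the sentences do?** The imputation sentence is in the future tense and names the one-sided 95% bound. The bootstrap sentence is in the present tense, gives a value and prescribes nothing. The bootstrap appears nowhere else.

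**4. How far apart are the two constructions?** Take n = 45, SD 35 and 10% missing, with about 40 observed and the missing subjects left out of the bootstrap. Assume imputation leaves the mean unchanged.

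- Percentile-bootstrap margin: 1.645 × 35/√40 × √(39/40) = 8.99.
- Multiple-imputation margin: t(0.95, 44) × 35/√(45 × 0.9) = 1.680 × 5.500 = 9.24. The gap is 0.25 points.
- With Barnard–Rubin degrees of freedom (20 imputations, df 36.9) the margin is 9.30. The gap is 0.31 points.

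Over n = 40–48 and SD 30–40 the gap runs from 0.22 to 0.42 points with n−1 degrees of freedom, and from 0.27 to 0.50 with Barnard–Rubin. In a simulation of 5 settings × 600 = 3,000 normal data sets the mean gap was 0.39–0.54 and the largest 3.0. A separate simulation bootstrapped the full sample and inflated the imputation standard error for 10% missing information. With normal and left-skewed data and SD 20–40, it gave average gaps of about 0.2–1.0 points.

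**5. Could imputation shift the mean enough to matter?** With 10% missing, the mean moves by 0.1 × d, where d is the average shortfall of imputed against observed values. To use up 25.8 points by this route alone, d would have to be 25.8/0.1 = 258 percentage points. This check applies only if 50.8% is a result of this trial.

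**6. Does the side matter?** One-sided and two-sided 95% t limits differ by 1.45 points (n = 48, SD 30) to 2.14 points (n = 40, SD 40). That affects how 50.8% is read. It does not affect the decision bound, whose side the analysis section states.

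**The case for a change.** The strongest case for a change is that this is the trial's only effectiveness hypothesis. Its bound should have one traceable method, and any value printed beside it should be identifiable. The Protocol Summary names only the bootstrap, and no link is drawn between 50.8% and the sample-size section. Even if the number is a planning value, it sits unlabelled inside the success criterion in two places. Correcting that would take a few words.

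The factual part stands: the source, sample size and role of 50.8% are not given, and a label would help a reader. The inference to two constructions does not stand. It assumes that unless 50.8% is a planning value it must be a competing decision bound, yet a supportive bootstrap result would leave the stated method untouched. A summary table that omits detail given in the analysis section does not create a second rule. Nor is a plan at fault for failing to show which bound was finally used, since that belongs in the study report.

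The numerical comparison has a limit of its own. Holding the mean unchanged removes the main way in which the two methods could diverge, so the small gaps are illustrative. The conclusion rests on the wording of the instruction more than on these figures.

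**Conclusion.** The concern does not call for a change. An analyst following the plan would impute, pool, form the one-sided 95% lower limit from the pooled mean and standard error, and compare it with 25%. That is a sound and sufficiently specified analysis. The stray 50.8% is a labelling slip about where a number came from.

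The size is small: about 0.2–0.5 points between constructions under SD 30–40, n = 40–48, 10% missing and an unchanged mean, and up to about 1 point on average under the alternative set-up. Such a gap could matter only if the bound fell within a point or two of 25%. If 50.8% is this trial's limit, the margin is 25.8 points, or 4.1–6.0 standard errors (25.8/6.32 at n = 40, SD 40; 25.8/4.33 at n = 48, SD 30). If it is a planning value, it says nothing about this trial's result, and the stated rule applies as written. Labelling or moving the number would tidy the text but would alter no analysis or decision.

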## Evaluation of Safety Endpoint

The composite observed rate of post-procedure device related serious complications less than or equal to 15% at 3 months. Composite device related serious complications for this endpoint are 1) de Novo (new) severe urinary retention lasting more than 21 consecutive days post procedure, 2) formation of fistula between the rectum and urethra, and 3) perforation of the rectum or GI tract, 4) damage to ureter or ureteral orifices 5) damage to the trigone requiring surgical repair or 6) de novo, sustained erectile dysfunction.

The CEC will determine if any adverse events reported through 3 months post-index procedure qualify to meet the 6 elements of the composite safety endpoint. The observed rate of the six serious complications must be less than or equal to 15% for the trial to be successful.

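### Severe retention ended by a further procedure within 21 days of onset cannot count as an event in the 15% safety test

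*Combined protocol and SAP*

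**What the plan says.** Evaluation of Safety Endpoint makes the composite a condition of trial success: "The observed rate of the six serious complications must be less than or equal to 15% for the trial to be successful". Element 1 is "de Novo (new) severe urinary retention lasting more than 21 consecutive days post procedure", and the Protocol Summary words it the same way: "De Novo (new) severe urinary retention lasting more than 21 consecutive days post procedure". The other elements are rectourethral fistula, perforation of the rectum or GI tract, ureteral damage, and "damage to the trigone requiring surgical repair or 6) de novo, sustained erectile dysfunction". The committee's task is tied to this list: "The CEC will determine if any adverse events reported through 3 months post-index procedure qualify to meet the 6 elements".

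Two sections deal with a second procedure.

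- **Intention to Treat Group**, which covers the endpoints, says that "primary outcome data from subjects retreated with either the UroLift System or with any other surgical procedure will be censored", effective the day after the procedure.
- **Safety Group** keeps all data "unless a non-UroLift BPH surgical procedure (e.g. TURP, Laser, HOLEP) is performed", and then censors on the day of surgery. That section applies only to safety analyses other than the safety endpoint.

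Neither section sets an earliest date for a second procedure or mentions retention. Analysis of Success Measures keeps every subject in the intention-to-treat analysis of the primary endpoints. On size, the Protocol Summary states: "A total of no more than 48 subjects (minimum of 40) will be enrolled".

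**The concern.** A further procedure that relieves retention also stops the clock on which the endpoint depends. Take two men with the same severe retention starting at implantation. One is still in retention on day 22 and is counted. The other has a further procedure on day 15 that relieves him; his retention lasted at most 15 days and he is not counted. The difference comes from when someone intervened, not from what the device did.

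Element 5 shows that the composite can use the need for surgery as a criterion, since trigone damage counts only if it requires surgical repair. For retention, a further procedure has the opposite effect and prevents the count.

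At stake is a success criterion decided on a point estimate in 40 to 48 men, where one event can change the result. Enrollment requires an enlarged median lobe contributing to obstruction, so retention after the procedure is a natural safety question for this population.

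**Working it through.** **1. Can the man be counted?** Let retention start on day *s* and be ended by a procedure on day *t*. Its duration is at most *t* − *s*. Element 1 needs a duration above 21 days, so it cannot be met when *t* − *s* ≤ 21. If retention starts at the procedure (*s* = 0), the boundary is day 21; with later onset it moves later by the same amount. If retention continues through the second procedure and passes 21 days, the element can still be met, provided the data are not censored.

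**2. Does any other rule count him?**

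| Rule | Effect on this man |
|---|---|
| Elements 2 to 6 | None is reintervention or retention |
| CEC review through 3 months | Applies the six elements as listed |
| Intention to Treat Group | Censors after the procedure; creates no event |
| Safety Group | Does not govern the safety endpoint; also only censors |
| Analysis of Success Measures | Points to his staying in the denominator |

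He therefore adds 0 to the numerator unless another element occurs.

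**3. The 15% limit in whole events.** The plan gives no derivation of 15%, so there is no calculation to reproduce. The largest *k* with *k*/*n* ≤ 0.15 is 6 for *n* = 40 to 46 and 7 for *n* = 47 to 48.

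| *n* | Most events that pass | One more event | Weight of one man |
|---|---|---|---|
| 40 | 6/40 = 15.0% | 7/40 = 17.5% | 1/40 = 2.5 points |
| 48 | 7/48 = 14.6% | 8/48 = 16.7% | 1/48 = 2.1 points |

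One uncounted man can separate 7/40 (fail) from 6/40 (pass). Two can turn 8/40 = 20.0% into 15.0%, or 9/48 = 18.8% into 14.6%.

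The plan does not say how a censored man enters the denominator. If he were dropped, the comparison would be 6/39 = 15.4% against 7/40 = 17.5%, or 7/47 = 14.9% against 8/48 = 16.7%. The rate is lower than if he were counted in either case.

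**4. Illustration with assumed rates.** The chance of passing is the exact binomial P(X ≤ *k*), with *k* = 6 at *n* = 40 and *k* = 7 at *n* = 48. Assume a counted-event rate of 5% or 10%, plus a separate rate *h* of uncounted retention in men with no other composite event. As written, the probability uses the counted rate alone; with the clause it uses the counted rate plus *h*.

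| *n* | Counted rate | As written | Clause, *h* = 2% | *h* = 5% | *h* = 10% |
|---|---|---|---|---|---|
| 40 | 5% | 0.997 | 0.980 | 0.900 | 0.607 |
| 40 | 10% | 0.900 | 0.802 | 0.607 | 0.286 |
| 48 | 5% | 0.998 | 0.983 | 0.898 | 0.567 |
| 48 | 10% | 0.898 | 0.787 | 0.567 | 0.229 |

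With *h* = 0 nothing changes. No rate in this table comes from the documents.

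**The case against.** The best defence is that a duration threshold is a legitimate choice: it counts persistent retention and leaves out the transient kind. The second-procedure rules are general provisions for 12 months of follow-up, and setting no earliest date does not show that surgery within three weeks is expected. Entry criteria exclude current retention, residual urine above 250 mL and neurogenic or atonic bladder, which narrows the group at risk. The CEC charter is not among the documents and may already cover the case.

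Most of this stands as a limit on size. It does not close the gap: retention that had to be ended by a procedure has not been shown to be transient, and the endpoint text gives the CEC no ground to count it.

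A reader might infer more than the documents support:

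- **That the man counts as free of complications.** He has no composite event. Adverse events and interventions are still collected at every visit, and retention that began before the second procedure remains reportable.
- **That all retention operated on before day 22 escapes.** That boundary holds only for onset at the procedure, and only if the second procedure ends the retention.
- **That the worst retention is the kind left out.** Timing may reflect site practice as much as severity; the documents do not say.
- **That the trial's rate is in fact biased.** This depends on such cases occurring.

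**Conclusion.** The gap is real and follows from the wording: element 1 can be met only by duration, and nothing elsewhere in the documents corrects for a procedure that cuts the retention short. Applied exactly, the rule can only lower the observed rate relative to counting these men, by 2.5 points each at 40 subjects or 2.1 at 48 if they stay in the denominator.

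The conclusion rests on retention being severe, new and unresolved at the second procedure, on that procedure ending it within 21 days of onset, and on no other element occurring. The frequency is unknown and may be zero, so no actual bias in this trial has been shown. It is a cheap improvement worth making because single events decide the criterion.

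**What to change.** In the Protocol Summary and in Evaluation of Safety Endpoint, keep the 21-day threshold and add a second route to element 1: de novo severe retention that is unresolved when a UroLift retreatment or other BPH surgical procedure is performed within the 3-month window meets the element, even if that procedure cuts it short of the threshold. Add that the censoring under Intention to Treat Group does not remove such a man from the numerator or denominator of the safety endpoint. The CEC would still judge whether the retention was new, severe and device related, so a brief or unrelated episode would not count automatically.

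This changes counting only, not how any patient is managed. Retention that resolves without a further procedure within 21 days stays uncounted. The cost is one clause in two places, one sentence on censoring, and a matching line in the CEC charter. The Summary of Procedures already schedules adverse events, catheterization and intervention review through 3 months. The downside is that the observed rate may be slightly less favourable.

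### Does the 15% safety criterion need a stated denominator and a rule for subjects whose 3-month status is unknown?

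*Combined protocol and SAP*

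**What the plan says.** Trial success depends on a point estimate: "The observed rate of the six serious complications must be less than or equal to 15% for the trial to be successful". Under Evaluation of Safety Endpoint, the clinical events committee (CEC) decides "if any adverse events reported through 3 months post-index procedure qualify to meet the 6 elements" of the composite. That fixes the numerator. The section does not name the denominator and does not mention subjects who leave or miss the visit before 3 months.

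The denominator has to be read from other sections:

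- Intention to Treat Group puts the main analyses, endpoints among them, on ITT and adds: "All subjects who are enrolled will be included in the intention to treat analysis".
- Safety Group sets the safety endpoint apart from its own scope: "Any safety analysis, outside of safety endpoint, will be performed on the" Safety Group.
- Analysis of Success Measures keeps all subjects in the ITT analysis of the primary endpoints, whether or not the procedure succeeded.

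One sentence pulls the other way, under Intention to Treat Group: "The IIT population is used for efficacy analyses". The only missing-data rule in the plan is multiple imputation of the 6-month IPSS change. No sensitivity analysis is given for the safety rate.

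**The concern.** An all-enrolled denominator combined with a numerator of reported events treats a subject lost in week 2 as free of every later complication. Compared with complete follow-up, that can only lower the observed rate.

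Two components need time to show themselves: "severe urinary retention lasting more than 21 consecutive days post procedure" and "de novo, sustained erectile dysfunction". The second relies on questionnaires scheduled at 1 and 3 months. Effectiveness has a rule for loss to follow-up and safety has none, although both decide trial success.

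The limit is a small count, so one or two unknown subjects could decide a result close to it. Because one sentence ties ITT to efficacy, an analyst might also divide by evaluable subjects only and reach a different verdict from the same data. The ITT section also has a censoring rule for retreatment ("primary outcome data from subjects retreated with either the UroLift System or with any other surgical procedure will be censored the day after"), and nothing expressly switches this off for the safety endpoint.

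**Working it through.** **Inputs.** The limit is 15% (Evaluation of Safety Endpoint). Enrollment is N = 40 to 48 (Protocol Summary). The documents give no number of unknown subjects (m), no true complication rate (p) and no rate among the unknown (q). I assume m = 2, p from 5% to 15%, and q = p or q = 3p.

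**Limit as a count.** The 15% is a set threshold, so there is no derived figure to reproduce. The largest passing count is L(N) = floor(0.15 × N):

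- N = 40: 6.0, so 6. N = 46: 6.9, so 6.
- N = 47: 7.05, so 7. N = 48: 7.2, so 7.

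**Three scorings with 2 unknown, at the largest passing count.**

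| N | Events | All enrolled | Evaluable only | Worst case |
|---|---|---|---|---|
| 40 | 6 | 6/40 = 15.0%, pass | 6/38 = 15.8%, fail | 8/40 = 20.0%, fail |
| 45 | 6 | 6/45 = 13.3%, pass | 6/43 = 14.0%, pass | 8/45 = 17.8%, fail |
| 48 | 7 | 7/48 = 14.6%, pass | 7/46 = 15.2%, fail | 9/48 = 18.8%, fail |

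The all-enrolled and evaluable-only limits, L(N) and L(N − 2), differ only at N = 40, 41, 47 and 48. At N = 42 to 46 both are 6. Under worst case, one unknown is enough to reverse a pass at the largest passing count. With at most 4 events at N = 40 to 46, or 5 at N = 47 or 48, two unknowns cannot change the verdict (4 + 2 = 6; 5 + 2 = 7).

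**Chance of passing.** Let X ~ Bin(N − 2, p). All enrolled passes if X ≤ L(N), evaluable only if X ≤ L(N − 2), worst case if X ≤ L(N) − 2. Ranges are over N = 40 to 48.

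| True rate | All enrolled | Evaluable only | Worst case |
|---|---|---|---|
| 5% | 99–100% | 99–100% | 93–98% |
| 8% | 94–98% | 91–96% | 73–85% |
| 10% | 85–92% | 81–90% | 55–71% |
| 15% | 50–66% | 45–61% | 19–31% |

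**Chance of a wrong pass.** Worst case is a bound, since it gives both unknown subjects an event. The error that matters is a pass that complete follow-up would have made a fail: P(X ≤ L(N) and X + Y > L(N)), with Y ~ Bin(2, q).

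Example with N = 40 and p = q = 10%: P(X = 6) = 0.0948 and P(X = 5) = 0.1551. The chance is 0.0948 × (1 − 0.9²) + 0.1551 × 0.1² = 0.0180 + 0.0016 = 0.0196, or 2.0%.

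| True rate | q = p | q = 3p |
|---|---|---|
| 5% | 0.05–0.16% | 0.2–0.5% |
| 10% | 1.7–2.6% | 5.4–8.2% |
| 15% | 4.8–5.2% | 14.5–15.7% |

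**How unknown a lost subject would be.** Summary of Procedures and its notes place a post-procedure cystoscopy and a digital rectal examination, the latter to rule out implantation in the rectum, at the index procedure. Acute damage can therefore be looked for before release. If a month is taken as 30 days, the 1-month visit opens at day 30 − 7 = 23, so retention that began at the procedure can be judged there. A subject lost between months 1 and 3 is mainly unknown for sustained erectile dysfunction and late events.

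**Retreatment censoring.** The safety section has the CEC review adverse events through 3 months and makes no exception for retreated subjects. That specific text is the natural guide for this endpoint.

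**The case for a change.** The best case for a change is that it is cheap. One paragraph and one corrected sentence would name the denominator, report how many subjects lack 3-month status, and show evaluable-only and worst-case rates. No subjects, visits or data would be added. It would also close off a choice of denominator after the data are seen, on a criterion that decides the trial, and at both ends of the enrollment range that choice can change the verdict.

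Parts of this stand. The denominator is not named in the safety section, the efficacy sentence is loose, and a pass at exactly 6 or 7 events would deserve a look at who was lost.

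The argument also needs two readings that do not fit together. If the population sections settle ITT, the rule is fixed (adjudicated events over all enrolled) and an evaluable-only analysis would depart from the plan. If they do not, the plan does not score unknown subjects as complication-free. Nowhere does it say so; that is an inference from the ITT reading. The contrast with IPSS shows no inconsistency either, because a continuous score at a fixed visit and a count of adjudicated events ordinarily need different handling.

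The added wording would keep the very convention under criticism. It would also raise a new question: enrolled but untreated subjects cannot have a post-procedure event, yet a worst-case rule could count them as having one.

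**Conclusion.** No change follows. This is missing detail that an analyst would fill sensibly from the rest of the plan: all enrolled in the denominator, CEC-adjudicated events through 3 months in the numerator. Writing it down would leave the count, the 15% limit and the chance of passing where they are. The extra rates would carry no decision, and a reader can obtain them from the event count and the number followed.

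With 2 unknown subjects at the same risk as the rest, a wrong pass has a chance of at most 0.16% at a true rate of 5% and at most 2.6% at 10%. The largest figures, 14.5–15.7%, need a true rate at the limit itself and three times that rate among those lost. At that true rate the criterion passes 50–66% of trials with 2 unknown in any case, because it is a point estimate.

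The conclusion rests on few subjects being lost by 3 months, which the documents neither support nor contradict. With many lost and a count at 6 or 7, the result should be read with caution, but that is a matter for the report.
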